| Group C Diabetic test Early onset of Diabetes mellitus receiving polyherbal formulation 1800mg in two divided doses for six weeks | Dietary Supplement: Polyherbal formulation Test candidate will be administered per oral before / with meal in two divided doses |

Study Description:

Brief description:

Primary protocol to this study is to develop a natural remedy to prevent diabetes mellitus in pre-diabetic state and elaborate the effectiveness of polyherbal formulation for carrying out Phase-II, III and IV. It also aimed at to see the level of difference of glucose tolerance and impaired fasting glucose and impaired glucose tolerance between pre-diabetic and diabetic to evaluate the potential benefit for treatment of insulin resistance and sensitivity. To see the for prevention of Diabetes Mellitus (DM) and stopping / delaying the onset of DM.

Detailed description:

This study is a clinical trial study to evaluate the potential of prevention in pre-diabetics and to prevent onset of diabetes mellitus. For this purpose, volunteers will be enrolled in the study by observing the Helsinki Declaration for clinical trials.

volunteers will be screened for the impaired glucose tolerance or impaired fasting glucose or at risk to develop diabetes mellitus type 2.

On screening, pre-diabetics and early onset diabetics with no previous history of treatment etc will be grouped into A and B.

Biochemical evaluations will be carried out at base line and followed by three weeks intervention and evaluation of biomarkers and at sixth week for further evaluation.

Collected data will be evaluated for primary out comes and secondary out come. statistical analysis will be done.

Method:

Step 1: Consent, observation of Ethical Principles of Declaration of Helsinki, questionnaire and screening of targeted population for impaired fasting glucose (IFG) and impaired glucose tolerance(IGT), (16-17)

State FPG Level 2-h plasma glucose

In OGTT (mg/dl)

Impaired Fasting Glucose = 100-125 <200

Isolated IFG = 100-125 <140

Impaired Glucose Tolerance = <126 140-199

Isolated IGT = <100 140-199

Step 2: Individuals with IFG & IGT evaluated for age, family history of diabetes in first degree relation, BMI = 35 kg/m³ will be evaluated for following profiles on two week basis with baseline

1. Lipid profile for elevated triglycerides, low HDL, Cholesterol
2. Hepatic functions: SGPT, SGOT, ALT,
3. Renal Function test for Creatinine, Urea
4. Insulin level

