Step 3: At high risk population with impaired FG & IGT and underlying or corresponding diseases ,(8-11) population will be given oral polyherbal formulation of Eastern Medicine for six weeks.

Step 4: data collected and interpreted with statistical significance

Eligibility Criteria:

| | |
|-----------------------------|---|
| Study Population: | 
• community samples will be obtained from the area of Bahawalpur• Model Town A, B, and• remote areas of district Bahawalpur consisting of Khairpur Tamewali city population |
| Sampling Method: | Probability Sample |
| Minimum Age: | 18 Years |
| Maximum Age: | 59 Years |
| Sex: | All |
| Gender Based: | No |
| Accepts Healthy Volunteers: | Yes |
| Criteria: | Inclusion Criteria: 
• Age: 18-59• Impaired Fasting Glucose (100-125mg/dl) |

- Impaired Glucose Tolerance (140-199mg/dl) 2h-75gm OGTT
- History of Diabetes in first degree relation with one condition
- At high risk with BMI > 35%
- Early onset diabetic / accidental on screening (glucose >200mg/dl)

Exclusion Criteria:

- on renal dialysis;
- an acute or terminal illness or serious mental illness;
- history of recent coronary event within the last 12 months;
- a recent history of acute medical problem or admission to hospital;
- any other severe medical conditions that need intervention / treatment
- has poor short-term prognosis (expected death in <2 years);
- is planning to travel for longer than 6 weeks during the 6-week intervention period; or
- is with compromised liver / kidney / cardiac function
- older patients of DM taking any form of medication / intervention

Out Comes:

Study outcomes will be measured by various biomarkers and beneficial effects / toxic effect will be assessed by certain blood biomarkers as followed.

Primary outcomes:

1. Enhancement of Glucose Tolerance
2. Enhancement of Impaired Fasting Glucose Tolerance
3. HbA1c level of reduction

Secondary Outcomes:

1. Lipid Profile including
 - a. Level of Cholesterol
 - b. Triglycerrhides
 - c. Low density lipid (LDL)
 - d. High density lipid (HDL)

Unspecified Outcomes:

1. Liver Function
 - a. Serum Glutamate Oxaloacetate Transaminase (SGOT) level
 - b. Serum Glutamate Pyruvate Transaminase (SGPT) level
 - c. Alkaline Phosphatase level

2. Kidney Function
 - a. Serum Creatinine level
 - b. Blood Urea Nitrogen level

Noting of Adverse events:

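### The diabetic entry criterion has no upper glycaemic limit, and no glucose value at week 3 or week 6 triggers referral or withdrawal

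*Protocol*

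**What the plan says.** **Entry.** The inclusion criteria (Protocol, Eligibility Criteria) bound both pre-diabetic states: 100 to 125 mg/dl for impaired fasting glucose and 140 to 199 mg/dl at 2 hours for impaired glucose tolerance. The diabetic line reads "Early onset diabetic / accidental on screening (glucose >200mg/dl", with no upper value and no stated sampling condition. The Detailed description adds that these are "early onset diabetics with no previous history of treatment etc", and the last exclusion line removes established patients already on treatment.

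**Treatment.** The group table describes Group C as "Early onset of Diabetes mellitus receiving polyherbal formulation 1800mg in two divided doses for six weeks". No background or rescue treatment is described. The Brief description says the trial is to "elaborate the effectiveness of polyherbal formulation for carrying out Phase-II, III and IV", so the product's effect is still to be established.

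**Follow-up.** Biochemical evaluation takes place at baseline, "followed by three weeks intervention and evaluation of biomarkers and at sixth week for further evaluation". Separately, Method, Step 2 says that people with impaired fasting glucose and impaired glucose tolerance "will be evaluated for following profiles on two week basis with baseline". The profiles listed there are lipids, hepatic function, renal function and insulin.

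**Adverse events.** The only instruction is to categorise them with the MedDRA dictionary.

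**The concern.** Under the group table, the people in Group C have just been found to be diabetic, have never been treated, and are given a product whose benefit the trial sets out to explore. For such people a protocol would normally say how high glucose may be at entry and what glucose value on study ends the experiment for that person. This Protocol says neither. Followed as written, it treats every value above 200 mg/dl alike, both at the door and at the two later evaluations.

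What is at stake is participant safety: up to six weeks of marked hyperglycaemia during which no rule calls for established treatment. Such treatment is not forbidden, but nothing in the plan prompts it. These are rules on entry, referral and withdrawal, which belong in a protocol, so a statistical analysis plan that is not at hand would not be expected to supply them.

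**Working it through.** The Protocol gives no figure to reproduce on this point, so the check is a reading of the relevant places side by side.

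1. **Entry line.** The two pre-diabetic criteria each have a lower and an upper value. The diabetic criterion has one value, a lower bound of 200 mg/dl. No HbA1c limit appears anywhere in the eligibility section.

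2. **Exclusion lines.** There are nine: dialysis; acute, terminal or serious mental illness; recent coronary event; recent acute problem or admission; other severe conditions needing treatment; poor short-term prognosis; long travel; compromised liver, kidney or heart function; treated diabetes.
   - Lines giving a glucose or HbA1c limit: 0 of 9.
   - Lines naming type 1 diabetes or ketosis: 0 of 9.
   - Lines naming diabetes at all: 1 of 9, and it removes treated patients, which leaves the untreated ones.

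3. **Could the severe-conditions line act as a ceiling?** If untreated diabetes as such counted as a severe condition needing treatment, the line would empty Group C. If it does not count, the line leaves the screener to decide at what glucose it begins to apply. It therefore gives discretion but no boundary.

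4. **On-study checks.** The Detailed description names two after baseline, at weeks 3 and 6. The primary outcomes are glycaemic (glucose tolerance, fasting glucose, HbA1c), so glucose will presumably be measured, although the sentence that sets the schedule does not name it. Checks with a glucose value that leads to action: 0 of 2.

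5. **Step 2 profiles.** Four are listed and none is glucose or HbA1c (0 of 4). The two-weekly schedule therefore supplies no glycaemic check even if it is read as covering Group C.

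6. **What already exists for a fix.** Step 1 screening uses fasting and 2-hour glucose (its table is headed "State FPG Level 2-h plasma glucose"), and a glucose reagent kit is on the materials list. No HbA1c kit and no ketone test are on that list.

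The counts in steps 2, 4 and 5 establish what the text does not contain. They do not measure harm. The number of volunteers who would enter with very high glucose depends on the screened population, for which the Protocol gives no distribution.

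**The case against.** The strongest reply is that the door is not as open as it looks. Group C is also limited by age (18 to 59), by detection at screening, by absence of previous treatment, and by exclusion of compromised liver, kidney or cardiac function. The severe-conditions exclusion turns on severity and need for treatment, not on visible illness, so a screener faced with a very high result or suspected type 1 diabetes could use it. The trial is also placed under the Declaration of Helsinki. All of this stands. It follows that a reader should not infer that glucose is the only thing that limits entry, or that only the visibly ill would be kept out; the text supports neither. What remains is a lack of specificity: none of these provisions gives a glucose value, so two screeners could lawfully decide differently about the same person.

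The Protocol is also loose about populations. Step 2 is written for people with impaired glucose regulation, but so is Step 3, the dosing step, although the group table clearly doses diabetics. It would be unfair to lean on that wording to set the two-weekly schedule aside. The better reason is that its list contains no glucose measure.

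Type 2 diabetes is the evident target from the objectives, and the 2-hour condition can largely be inferred from the Step 1 table. Stating them, and naming suspected type 1 diabetes and ketosis as exclusions, are therefore clarifications.

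Finally, consent material is not at hand. A reader might infer that participants are given no instruction to report symptoms, but such instructions commonly sit in participant information, and their absence cannot be shown.

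**Conclusion.** The point holds as a safety improvement that should be made. The diabetic entry rule has no glycaemic ceiling and the on-study evaluations have no glucose action value, so the plan as written permits six weeks on the product alone for an ambulatory, untreated person with marked hyperglycaemia. Its size in participants is unknown. The conclusion assumes that the group table describes who is treated and that no unseen protocol text adds a limit.

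Two stronger inferences should be resisted:

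- Week 3 is day 21 of 42, and a reader might conclude that a week 3 stop would halve the harm. Dosing days measure exposure to the product, whereas the risk here is untreated hyperglycaemia. Stopping the product does not treat that; referral does.
- A reader might conclude that the comparison of Group A with Group B is untouched. That is so under the group table, where diabetics form Group C. The Detailed description, however, places screened pre-diabetics and early-onset diabetics together in groups A and B. On that reading diabetics could be in the compared groups, including the placebo group. The documents do not settle which applies.

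**What to change.** **Entry.** Before enrolment, add to the diabetic inclusion line a numeric upper limit for fasting plasma glucose, set by the responsible clinicians, and state that anyone above it is referred for treatment. The Protocol offers no basis for a particular value, so none is proposed here. Fasting glucose is the natural choice because screening already uses it.

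**On study.** Name fasting glucose in the week 3 and week 6 evaluations and give it an action value, confirmed by a repeat sample. Set it separately from the entry ceiling; otherwise someone enrolled just below the ceiling could be withdrawn on ordinary fluctuation. Above it at week 3: stop the product and refer. Above it at week 6: refer.

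**Data.** Record any diabetes treatment started, with its date, and still take the week 6 measurements.

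**Clarifications.** State that the line means newly detected type 2 diabetes, give the sampling condition for the 200 mg/dl value, and exclude suspected type 1 diabetes or ketosis.

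**Cost.** A short protocol amendment. The scheduled evaluations and the listed glucose kit are enough apart from the confirmatory repeats and, where ketosis is suspected, a ketone test that is not on the materials list. Expect some more screen failures and withdrawals among diabetics, in a number that the Protocol does not allow one to estimate. In anyone who starts treatment, the week 6 values will no longer reflect the product alone.

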5. To evaluate the preventive efficacy of polyherbal formulation(test) by assessing the effect on Glucose intolerance.
6. To evaluate effect of polyherbal formulation (test) on the insulin.

7. To evaluate the potential preventive effect of polyherbal formulation for developing a preventive strategy for prevention of DM.

Material and Method:

Chemicals:

Liver function test kit

Renal function test kit

Lipid profile kit

Insulin kit

Glucose Reagent Kit

Glucose (pharmaceutical grade)

Polyherbal formulation:

In the last few years, there has been an exponential increase in the field of herbal medicinal study which is ahead of popularity both in the developing and developed countries for the reason of their natural origin and less side effects (4).

Despite extensive progress in the treatment of diabetes by oral hypoglycemic agents, the exploration for newer drugs continues because of the several restrictions found in the usage of synthetic drugs. Medicinal plants supply a potential source of hypoglycemic drugs possessing the dynamic compounds which have been used in the treatment of diabetes and they are highly praised for their therapeutic properties in the traditional medicine system.(5) Polyherbal formulation of Eastern Medicine used in this research is popularly utilized in traditional medicine in various countries to control and treat diabetes. These herbs are used extensively. Four important herbs among these are selected for the preventive effect of these products. These includes Colosynth seed, Occimum tenuiflorum seed, Holarrhena antidysenterica seeds, Gymnemia Sylvester leaves. These herbs have proved to produce anti-diabetic effect by modulating beta-cell in pancreatic islet cell, enhanced insulin secretion, hypoglycemic, anti-hyperlipidemic, anti-Cholesterolic effects on CVS and diabetes. (18-21)

Study Design:

Three arm parallel Observational Cross-Sectional and Case-Crossover clinical trial (Phase 1)

Groups:

Groups and Interventions

| Groups/Cohorts | Interventions |
|--|--|
| Group A Pre-diabetic placebo Group of pre-diabetics receiving placebo BD for six weeks | |
| Group B Pre-diabetic test Group of Pre-diabetic receiving polyherbal / test candidate 900mg in two divided doses for six weeks | Dietary Supplement: Polyherbal formulation Test candidate will be administered per oral before / with meal in two divided doses |

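### The travel exclusion can never be met as written, and on a looser reading it still admits volunteers who will be away for every post-baseline evaluation

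*Protocol*

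**What the plan says.** Under Eligibility Criteria, the exclusion list bars anyone who "is planning to travel for longer than 6 weeks during the 6-week intervention period". The other exclusions concern dialysis, illness, recent coronary events or hospital admission, other severe conditions, prognosis, organ function and treated diabetes. None deals with planned absence.

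The intervention lasts six weeks throughout. Method, Step 3 states that the "population will be given oral polyherbal formulation of Eastern Medicine for six weeks". The Groups table gives the same length for all three groups; for Group A it reads "Group of pre-diabetics receiving placebo BD for six weeks".

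The protocol gives two evaluation schedules:

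- The Detailed description has a baseline assessment "followed by three weeks intervention and evaluation of biomarkers and at sixth week for further evaluation", that is, weeks 3 and 6.
- Method, Step 2 says that people with impaired fasting glucose and impaired glucose tolerance "will be evaluated for following profiles on two week basis with baseline". The list that follows covers lipids, liver tests, kidney tests and insulin.

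The primary outcomes are glucose tolerance, fasting glucose and HbA1c. The Step 2 list names none of the three.

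**The concern.** The threshold equals the length of the period it applies to. A rule that requires more than 6 weeks of travel within 6 weeks has no one to exclude, and it is the only listed criterion that touches on availability.

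All three primary outcomes need a post-baseline measurement. Safety judged from blood markers is itself an objective (Objective 4), in a trial labelled Phase 1. A volunteer known at screening to be away from week 3 to week 6 could be enrolled and would then have no scheduled post-baseline evaluation under the week 3/week 6 schedule. Liver and kidney results would have gaps as well. An analysis plan can deal with missing values once they arise, but it cannot keep foreseeable absentees out of the trial.

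**Working it through.** **Inputs**

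- Intervention period: 6 weeks = 6 × 7 = 42 days (Groups table; Method, Step 3).
- Exclusion threshold: travel of more than 6 weeks, so more than 42 days (Exclusion Criteria).
- Schedule A: weeks 3 and 6 (Detailed description).
- Schedule B: every two weeks, so weeks 2, 4 and 6 (Method, Step 2).
- Assumption: baseline is day 0 and each visit falls on its nominal day. Schedule A is then days 21 and 42; schedule B is days 14, 28 and 42.

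**Literal reading: travel days inside the period**

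The largest possible number of travel days inside the period is 42. The condition 42 > 42 is false, so nobody can be excluded.

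**Loose reading: any trip of more than 42 days that overlaps the period**

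Some long trips are now caught, but every trip of 42 days or less passes. The shortest single absence that misses all post-baseline evaluations is last visit day − first visit day + 1.

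| Schedule | Visit days | Shortest absence missing all | Share of 42 days |
|---|---|---|---|
| A (weeks 3, 6) | 21, 42 | 42 − 21 + 1 = 22 days | 22/42 = 52% |
| B (weeks 2, 4, 6) | 14, 28, 42 | 42 − 14 + 1 = 29 days | 29/42 = 69% |

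Both absences are allowed on either reading.

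**Sensitivity to visit timing**

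- All visits one day later: A is 43 − 22 + 1 = 22 days and B is 43 − 15 + 1 = 29 days. Nothing changes.
- An assumed window of ±3 days (the protocol states none): A runs from day 18 to day 45, 45 − 18 + 1 = 28 days. B runs from day 11 to day 45, 45 − 11 + 1 = 35 days. Both are still no more than 42.
- In general, a window of ±k days adds 2k to the absence needed. It stays within the allowance while 22 + 2k ≤ 42 (k ≤ 10) for A, and while 29 + 2k ≤ 42 (k ≤ 6 in whole days) for B.

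**Week 6 alone**

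On nominal days, a trip of 1 day (2 days if visits fall a day later) is enough to miss the final evaluation.

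**The same traveller on both schedules**

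An absence from day 21 to day 42 misses both visits of schedule A. On schedule B it misses weeks 4 and 6 but not week 2.

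**The case against.** The strongest reply is that this is a slip in one line of eligibility text, with a hypothetical consequence. Harm requires a volunteer who plans at least 22 days away, timed across both visits, who does not come back for either, and whom staff enrol anyway. Passing the exclusion list does not oblige anyone to enrol a volunteer, and the consent material, which is not available here, may ask for availability. All of that is fair. It is why the point says only that such volunteers can be enrolled, and makes no estimate of missing data. The 52% and 69% are ratios of lengths and say nothing about bias or power.

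The purpose of the rule is also inferred, since the line mentions the intervention period and not visits; it might be meant to protect intake of the product. That is possible, but the rule does no better for that purpose, because a 42-day trip spanning the whole intervention also passes.

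The Step 2 schedule would give some travellers week-2 liver and kidney tests, so on that schedule the safety gap is partial (weeks 4 and 6). This stands. It is also true that the week 3/week 6 sentence does not name the primary outcomes; it speaks only of biomarkers. Linking it to them is a reasonable inference from the outcomes section, which says outcomes are measured by biomarkers, but it is an inference.

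Finally, the conflict between the two schedules exists whatever the travel rule says. It belongs here only because a rule tied to visits needs to know which visits are meant. None of these replies makes the criterion capable of being met.

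**Conclusion.** The concern holds. As written, the exclusion is empty. Read generously, it admits every trip of 42 days or less, whereas 22 days (weeks 3 and 6) or 29 days (every two weeks) is enough to miss all post-baseline evaluations. The emptiness follows from the protocol's own two figures and needs no assumption. The day counts assume visits on nominal days and a traveller who does not return for them. A one-day shift in visit placement or a ±3-day window does not change the conclusion.

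The effect on missing data cannot be sized, because the protocol gives no travel or dropout rate. The sponsor should correct the line; the point casts no doubt on the rest of the eligibility list.

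**What to change.** Replace the travel line with an exclusion, or a deferred start, for planned travel during the intervention period that would prevent attendance at the scheduled post-baseline evaluations, at minimum the one at week 6.

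Reconcile the Detailed description (weeks 3 and 6) with Method, Step 2 (every two weeks), and say at which visits the three primary outcomes are measured, so that the travel rule points to defined visits. Stating a visit window alongside would keep a trip of a day or two around week 6 from excluding someone needlessly.

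The cost is one line of eligibility text and the reconciliation of the two schedules, which is needed in any case. A few travelling volunteers would be deferred or not enrolled.

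### HbA1c reduction is one of three unranked primary outcomes, but the trial ends at six weeks, when only part of any HbA1c change would be visible

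*Protocol*

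**What the plan says.** Under Out Comes, the Protocol numbers three primary outcomes: "Enhancement of Glucose Tolerance", "Enhancement of Impaired Fasting Glucose Tolerance" and "HbA1c level of reduction". I read the second as fasting plasma glucose. None has a metric, an assessment time, a rank or a success rule.

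The Groups and Interventions table gives all three arms six weeks of treatment: "Group A Pre-diabetic placebo Group of pre-diabetics receiving placebo BD for six weeks" for the control arm, "in two divided doses for six weeks" for the pre-diabetic test arm, and "Early onset of Diabetes mellitus receiving polyherbal formulation 1800mg in two divided doses for six weeks" for the diabetic arm. The Detailed description sets biochemical evaluation at baseline, "followed by three weeks intervention and evaluation of biomarkers and at sixth week for further evaluation". Nothing later is scheduled. Step 4 of the Method has "data collected and interpreted with statistical significance". The Analysis entry is a heading only and gives no significance level.

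HbA1c appears nowhere else in the Protocol. It is absent from the seven objectives, the list of kits, the Step 2 laboratory profiles and the eligibility criteria. Objective 5, by contrast, ties preventive efficacy to the effect on glucose intolerance.

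**The concern.** HbA1c reflects glucose exposure over the life of the circulating red cells, so it moves gradually after glucose changes. A six-week trial sees only part of that movement, yet the Protocol gives HbA1c the same deciding weight as two measures that reflect current glucose directly. It gives no reason for doing so.

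The unranked list adds a second problem, because the Protocol does not say how the three results combine. If any one is enough, there are three chances of a false positive. If all three are needed, the outcome with the incomplete response can veto a real effect. The results are meant to inform later-phase work, so either misreading could carry forward: a promising preparation abandoned because of a diluted HbA1c result, or an inactive one advanced on a single chance finding.

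**Working it through.** The Protocol states no sample size, power, significance level, effect size or SD, so it has no figure to reproduce. The calculation uses the following inputs.

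- From the Protocol: three primary outcomes; treatment and last evaluation at six weeks, so t = 42 days.
- Assumed, because the Protocol gives no value: red-cell life L of 90 to 120 days, or HbA1c half-time h of 25 to 40 days; two-sided 5% per test; 80% power for the full HbA1c change; SD the same at week 6 as later; equal pairwise correlation among the three test statistics, from 0 to 0.9.

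**Share of the eventual HbA1c change visible at day 42, after a step change in glucose**

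Fixed-lifespan model, share = 1 − (1 − t/L)²:
- L = 90: 1 − (1 − 42/90)² = 1 − 0.284 = 0.716
- L = 105: 1 − (0.60)² = 0.640
- L = 120: 1 − (0.65)² = 0.578

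Half-time model, share = 1 − 0.5^(t/h):
- h = 25: 0.688
- h = 30: 0.621
- h = 35: 0.565
- h = 40: 0.517

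Over both models the range is about 52% to 72%.

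**Power and sample size when a share f is visible**

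Power = Φ(f × (1.960 + 0.842) − 1.960); sample-size multiplier = 1/f².

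| f | Power at week 6 | Sample-size multiplier |
|---|---|---|
| 0.517 | 30.4% | 3.74 |
| 0.578 | 36.6% | 3.00 |
| 0.640 | 43.4% | 2.44 |
| 0.716 | 51.8% | 1.95 |

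**False-positive rate if any one of three outcomes counts, each tested at 5%**

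- Independent: 1 − 0.95³ = 14.3%
- By simulation of three equicorrelated normal statistics (2 million draws): 13.6% at correlation 0.3, 12.5% at 0.5, 10.9% at 0.7, 8.4% at 0.9
- Perfect correlation: 5%

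**If all three must succeed**

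The false-positive rate is at most 5%. The chance of overall success cannot exceed the power of the weakest component. On the assumptions above, the HbA1c test alone caps it at about 30% to 52%, however well the two glucose outcomes perform.

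**With the two glucose outcomes only**

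Untreated multiplicity would give at most 1 − 0.95² = 9.75% if independent. A fixed order or Holm's procedure brings the overall rate to no more than 5%.

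**The case against.** A reader might infer that this trial runs a 14.3% false-positive rate. The Protocol does not support that. The figure needs each outcome tested at 5%, any single success to count, and independent tests. The Protocol states none of these, Step 4 is not a success rule, and measures of glucose control are unlikely to be independent. A multiplicity adjustment is also commonly left to the SAP, which is not at hand, so its absence is no finding. What stands is narrower: the Protocol itself chooses three co-equal primaries and does not say how they decide.

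A reader might also infer that HbA1c is uninformative at six weeks, or weaker than the glucose outcomes. Neither follows. Half or more of the change may already show, and the calculation compares HbA1c only with its own eventual change. Without SDs and effect sizes for the glucose measures, no ranking of power is possible. The week-3 evaluation gives no stronger argument, because no primary outcome is tied to week 3 and the Step 2 schedule differs and omits HbA1c. The turnover values are assumptions: the direction is firm across the range, the exact share is not.

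The Phase 1 label is a fair plea for less formality. It is weakened by the Protocol's own choice of efficacy outcomes as primary and its reliance on statistical significance.

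Finally, it is tempting to conclude that 2-h OGTT glucose should be the only primary. Eligibility admits impaired fasting glucose, and the Step 1 definitions include isolated impaired fasting glucose with a 2-h value below 140 mg/dl. Those participants have little room to improve on a 2-h outcome. Those with isolated impaired glucose tolerance (fasting below 100 mg/dl) have the mirror-image problem with a fasting outcome. Keeping both glucose outcomes is the better match to the population.

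**Conclusion.** The point holds, and the sponsor should act on it. The Protocol fixes a lagging marker as one of three co-equal deciding outcomes in a trial that ends at six weeks, and gives no reason for it. Under the assumed turnover, 80% power for the full HbA1c change becomes about 30% to 52% at week 6, so a null HbA1c result would say little.

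How much the unranked list matters depends on a rule the Protocol does not state. The false-positive rate is about 8% to 14% if any one success counts at 5% each, for correlations from 0.9 down to 0. If all must succeed there is no inflation, but HbA1c can mask a true effect. The choice and ranking of primary outcomes belong in the Protocol, so a later SAP does not remove the need to settle them there.

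**What to change.** In the Out Comes section:

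- Move HbA1c to the secondary outcomes and label the week-6 value as a partial, lagged response.
- Keep two primaries, each with its metric and time stated: change from baseline to week 6 in 2-h OGTT glucose, and change from baseline to week 6 in fasting plasma glucose, both for Group B versus Group A.
- State how they are tested: in a prespecified order, or with Holm's procedure at an overall 5%.
- Report Group C descriptively. It has no concurrent control with diabetes.

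The Group B versus Group A comparison relies on the Groups and Interventions table, where both groups are pre-diabetic. The Detailed description places pre-diabetics and early-onset diabetics together in A and B, and should be reconciled with the table in the same edit.

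The cost is Protocol wording only, provided that the OGTT is repeated at week 6, as the first primary outcome already implies. The small downside is that HbA1c can no longer carry a primary claim.
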